9.2 Sample size estimation

9.2.1 Cohort A

The sample size estimation is based on the primary endpoint of this study, all-cause mortality at 1 year post implant for patients having received a Portico Valve.

It is assumed that the expected mortality rate at 1 year post implant will be 22.1% ²⁰), and the total recruitment period will be 2 years; at least 608 patients are required to be at risk at 1 year post implant, in order to establish a two sided 95% confidence limit (18.8%, 25.4%) using non-parametric survival analysis with Peto's variance²¹. With a dropout rate of 10%, at least 866 patients need to be recruited.

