9.4 Secondary endpoint analysis

The secondary endpoint analysis will include both cohorts but results will be presented separately.

All safety secondary endpoints will be estimated using non-parametric survival analysis, and the data will be presented with the aid of Kaplan-Meier curve. The time to event will be defined as from the implant date to the first occurrence of the event for the patients who experienced the event, or to the last documented contact date for the patients without the event.

All safety secondary endpoints will be reported at 30 days, 1 year, 2 years, 3 years, 4 years and 5 years post implant, as recommended by VARC 2.

Note: Safety events which occurred prior to the index procedure will be reported separately and will not be included in the safety secondary endpoints reporting.

All continuous secondary endpoints will be summarized with the number of non-missing data, mean \pm standard deviation, median and range (minimum – maximum).

All categorical secondary endpoints will be tabulated with number of occurrence, and the percentage.

Generalized linear mixed model will be used to assess the evolution of the NYHA class at baseline, 30 days, 1 year, 2 years, 3 years, 4 years and 5 years post implant.

General linear mixed model will be used to evaluate the improvement for the QOL at baseline, 30 days, 1 year, 2 years, 3 years, 4 years and 5 years post implant.

Other secondary endpoints analysis will be described in a separate statistical analysis plan. This document will be available upon request.

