Technicians must be trained to recognize these problems and the appropriate responses. If a test is stopped for any of these reasons, the patient should sit or lie supine as appropriate depending on the severity or the event and the technician's assessment of the severity of the event and the risk of syncope. The following should be obtained based on the judgment of the technician: blood pressure, pulse rate, oxygen saturation, and a physician evaluation. Oxygen should be administered as appropriate.

CONTRAINDICATIONS

Absolute contraindications for the 6MWT include the following: unstable angina during the previous month and myocardial infarction during the previous month. Relative contraindications include a resting heart rate of more than 120, a systolic blood pressure of more than 180 mm Hg, and a diastolic blood pressure of more than 100 mm Hg.

Patients with any of these findings should be referred to the physician ordering or supervising the test for individual clinical assessment and a decision about the conduct of the test. The results from a resting electrocardiogram done during the previous 6 months should also be reviewed before testing. Stable exertional angina is not an absolute contraindication for a 6MWT, but patients with these symptoms should perform the test after using their antiangina medication, and rescue nitrate medication should be readily available. A deviation from the Clinical Investigation Plan will need to be collected if the patient is unable to complete this test.

LOCATION

The 6MWT should be performed indoors, along a long, flat, straight, enclosed corridor with a hard surface that is seldom traveled. If the weather is comfortable, the test may be performed outdoors. The walking course must be 30 m in length. A 100-ft hallway is, therefore, required. The length of the corridor should be marked every 3 m. The turnaround points should be marked with a cone (such as an orange traffic cone). A starting line, which marks the beginning and end of each 60-m lap, should be marked on the floor using brightly colored tape.

PROCEDURE

Required Equipment

- Countdown timer (or stopwatch)
- Mechanical lap counter
- Two small cones to mark the turnaround points
- A chair that can be easily moved along the walking course
- Worksheets on a clipboard
- A source of oxygen
- Sphygmomanometer
- Telephone
- Automated electronic defibrillator

Patient Preparation

- Comfortable clothing should be worn.

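### Section 9.4 has no rule for death or inability to walk in the NYHA, EQ-5D and 6MWT analyses, so apparent functional benefit can be overstated if sicker patients die sooner

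*Combined protocol and SAP*

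**What the plan says.** Section 9.4 (Secondary endpoint analysis) sets out the functional analyses in a few sentences.

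- **NYHA:** "Generalized linear mixed model will be used to assess the evolution of the NYHA class at baseline, 30 days, 1 year, 2 years", continuing annually to 5 years. Categorical endpoints are also tabulated as counts and percentages, with no denominator stated.
- **Quality of life:** "General linear mixed model will be used to evaluate the improvement for the QOL at baseline, 30 days, 1 year, 2 years", again continuing to 5 years.
- **6MWT:** no model is named, so it falls under the general rule: "All continuous secondary endpoints will be summarized with the number of non-missing data", plus mean, standard deviation, median and range.
- **Anything else:** other secondary analyses are left to a separate statistical analysis plan, which is not among the documents.

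Other sections determine what data can exist.

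- Section 7.4: death ends participation, so no later functional value is possible.
- Section 5.3.2: the clinical benefit endpoints are assessed where available, and EQ-5D is collected only through 1 year. Table 2 agrees on EQ-5D.
- Appendix G: "A deviation from the Clinical Investigation Plan will need to be collected if the patient is unable to complete this test". The same appendix has the distance, stopping time and reason written down when a walk is stopped early.
- Section 9.2.1: "It is assumed that the expected mortality rate at 1 year post implant will be 22.1" per cent.

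The documents give no estimand, composite, missing-data assumption or sensitivity analysis for these three endpoints.

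**The concern.** With about one implanted patient in five expected to be dead at 1 year, the handling of death largely determines what a functional result means. A mean 6MWT distance over non-missing values describes those alive, attending and able to walk. A mixed model fitted to NYHA or EQ-5D uses the earlier values of patients who later die, but its fitted mean at a late visit refers to a population in which nobody has died. If worse function goes with earlier death, both outputs can drift upward with no individual improving. Section 9.3 makes that link plausible: it lists NYHA class among the baseline factors to be examined for their relation to mortality.

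The study has no control arm in which the same selection would be visible, and Section 9.5 allows interim reporting of secondary endpoints and use of relevant data for reimbursement. A stable or rising functional curve could be read as durable benefit when part of it is attrition by death.

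**Working it through.** **Inputs from the documents (Section 9.2.1).** 1-year mortality 22.1%, so S = 0.779; 608 at risk at 1 year; two-sided 95% interval 18.8% to 25.4%; 10% dropout; 866 recruited.

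**1. The plan's own figure.** Half-width = 1.96 × √(S(1 − S)/Y) = 1.96 × √(0.779 × 0.221/608) = 0.0330, giving 18.8% to 25.4%. Solving for Y gives 0.779 × 0.221 × (1.96/0.033)² = 607.3, stated as 608. Recruitment: 608/0.779/0.9 = 867, against the stated 866. The sample size reproduces closely, so 22.1% is the working mortality assumption. No size or effect is stated for NYHA, EQ-5D or 6MWT.

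**2. Patients who can have a 1-year value.** 866 × 0.9 = 779. Expected deaths: 779 × 0.221 ≈ 172. Alive: about 607.

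**3. Drift in the survivor share (assumed model).** Latent severity b ~ N(0,1); logit P(NYHA III/IV) = −1.6 + 1.2b, constant over time, so no patient improves; constant individual hazard proportional to exp(γb), calibrated to 22.1% dead at 1 year. With everyone alive, 78% are in class I/II.

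| γ per SD (assumed) | Survivors in I/II, year 1 | Survivors in I/II, year 5 |
|---|---|---|
| 0 | 78% | 78% |
| 0.3 | 79% | 84% |
| 0.6 | 81% | 87% |

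A random-intercept logistic model fitted to 20,000 patients at γ = 0.6 gave 80% at year 1 and 84% at year 5. That is a rise of 4 points against 6 in the raw survivor share, so the model removes about a third of the drift.

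**4. Walking distance.** If patients who die by 1 year walked d metres less at baseline than survivors, the survivor mean at 1 year minus the baseline mean of all patients is raised by 0.221 × d: 5.5 m for d = 25 and 22.1 m for d = 100 (d assumed).

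An illustrative simulation gave every patient a true gain of 40 m and made death depend on function, leaving survivors 69 m better at baseline. Results:

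- survivor mean minus all-patient baseline mean: 55.1 m;
- paired change in survivors: 40.0 m;
- linear mixed model: 44.7 m.

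The mixed-model figure comes from one sample of 3,000. The same model gave 38.4 m when death was unrelated to function, so a metre or two is sampling noise.

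**5. A different question: death counted as failure.** If 70%, 80% or 90% of survivors are in NYHA I/II at 1 year (assumed), the share of all implanted patients alive in I/II is that figure × 0.779: 54.5%, 62.3% or 70.1%.

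**The case against.** Much of the opposing case stands, and it limits what can be claimed.

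- A reader might infer that the plan treats death and inability to walk as missing data. It does not say so. It is silent, and the separate analysis plan might fill the gap, although Section 9.4 defers only other endpoints to it. Missingness is what the named methods produce by default.
- A reader might infer that all three endpoints are analysed in survivors only. That fits the 6MWT summary. It does not fit the mixed models, which use earlier values from patients who later die, and for NYHA percentages no denominator is given.
- A reader might take the gap between 80% and 62.3% in step 5 as bias. It is not. Function while alive is a legitimate target in a single-arm study with no hypothesis for these endpoints; counting death as failure answers another question.
- A reader might infer that everyone who cannot finish the walk is lost from the mean. Early-stopped walks keep their distance, and nothing says a deviation removes a patient. Only those who cannot start, or for whom the test is contraindicated, have no value.
- Survival is hidden from no one: all-cause mortality is reported at the same time points, so the share alive and in NYHA I/II can be approximated by multiplication.
- EQ-5D stops at 1 year, so drift to 5 years does not apply to it.

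What the objections leave standing is that the target of these analyses is undefined and that no planned output sets function and survival side by side for the same patients.

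**Conclusion.** The point holds as a gap with a conditional consequence. Section 9.4 gives no rule for death or inability to walk. The 6MWT summary describes living, testable patients, and the mixed models describe function as if nobody had died. Apparent benefit can be overstated if sicker patients die sooner. The documents do not support saying that it is overstated.

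The size rests on assumptions outside the documents. Between years 1 and 5 the survivor share in NYHA I/II drifts by 0, about 5 and about 6 points at assumed log-hazards of 0, 0.3 and 0.6, with less drift in the mixed model. At 1 year the effect is small: 81% against an unchanged 78% in the strongest scenario. The 54.5% to 70.1% range belongs beside the survivor figure as a second description, not as a measure of its error.

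Separately, a quality-of-life model running to 5 years cannot be fitted as described when EQ-5D is collected only through 1 year. Section 9.4 must be reconciled with Section 5.3.2 and Table 2.

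**What to change.** 1. Keep both mixed models. Label their results as describing function while alive, and note that the fitted means carry an implicit projection for patients who have died.
2. At each visit, add a table over all implanted patients due for it, by cohort: alive in NYHA I/II, alive in NYHA III/IV, dead, alive but not assessed. Cohort B enters at 1 year or later, so its denominators must stay separate.
3. For 6MWT, record a reason whenever no distance is obtained. Report the numbers alive but unable to perform the test, and dead, beside the mean. Keep the recorded distance for walks stopped early.
4. Report EQ-5D through 1 year with the percentage dead beside it, and reconcile the 5-year quality-of-life model with the collection schedule.

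The cost is a few extra tables, one reason code on the case report form and a less favourable presentation of the functional results. No extra patients, visits or procedures are needed. It is a cheap improvement.

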9.5 Interim reporting

Interim reporting of primary and secondary endpoints will be performed, before the study's conclusion, upon recommendation of the steering committee.

Interim reporting of relevant data will also be performed for reimbursement purposes upon request of sponsor Health Economics and Reimbursement (HE&R) department.

10 Data Management

Overall, the sponsor will be responsible for the data handling. The sponsor and/or its affiliates will be responsible for compiling and submitting all required reports to governmental agencies. Investigational data will be analyzed by the sponsor and may be transferred to the sponsor's locations outside of Europe and/or any other worldwide regulatory authority in support of a market-approval application.

St. Jude Medical respects and protects personally identifiable information that we collect or maintain. As part of our commitment, SJM is certified to the U.S. - European Union Framework and U.S. – Swiss Safe Harbor Framework Agreements regarding human resources and patient clinical trial personal information.

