5.3.2 Secondary Endpoints

- Evaluation of the VARC-2¹⁹ defined event rates at 30 days, 1 year and annually through 5 years post implant. Definitions are detailed in Appendix D: VARC 2 Endpoints Definitions.
 - All-Cause Mortality
 - Cardiovascular Mortality
 - Myocardial Infarction
 - Stroke (disabling and non-disabling)
 - New or worsened conduction disturbances and cardiac arrhythmias (including pacemaker implantation rate at 30 days and new-onset atrial fibrillation (AF))
- Evaluation of the VARC-2¹⁹ defined event rates at 30 days from the index procedure.
 - Vascular access site complication (major and minor)
 - Bleeding (life-threatening, major and minor)
 - Acute kidney injury

- Prosthetic valve function at 30 days, 1 year and annually through 5 years post implant. (Includes prosthetic valve stenosis and prosthetic valve regurgitation).
- Clinical benefit endpoints at 30 days, 1 year and annually through 5 years post implant (if available)
 - NYHA functional classification
 - 6 Minute Walk Test (6MWT)
 - Quality of life measured with EQ-5D questionnaire through 1 year post-implant
- Evaluation of the TAVI-related resource utilization through hospital discharge (e.g. index procedural hospital/physician resources)
- Interim reporting at 30 days and 1-year all-cause mortality data may be performed on a subset of patients and compared with an appropriate external comparator. The results will be presented to appropriate agencies in France and in other countries where it will be deemed necessary for reimbursement purposes.

NOTE: Should new VARC or ESC Guidelines be published, endpoint analysis would be adjusted accordingly and analyzed to the extent that the previously gathered data supports the analyses based on the most current guidelines.

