6.2.4. Pre-Discharge visit (Cohort A only)

The pre-discharge visit will take place at the time of hospital discharge or within seven days after the index procedure, whichever occurs first. If the patient is expected to be discharged over the weekend, the discharge tests may be completed on the last week day prior to discharge. The assessment will include:

- Physical assessment
- Blood sample (between day 2 to 4 Post-implant or at discharge whatever occurs first) to obtain Hemoglobin, Creatinine and Troponin values
- 12 lead ECG (within 24hrs Post-implant and at hospital discharge but no later than 7 days Post-implant, whatever occurs first).
- Medication assessment
- Echocardiography (if a post-procedure echo has been done within 24 hours prior to discharge, an additional discharge echo is not required)
- NYHA functional classification
- QoL questionnaire (EQ-5D)
- Modified Rankin Scale
- Adverse events assessment
- Device Deficiency assessment
- Resource utilization assessment

6.2.5. 30 Day follow-up visit (Cohort A only)

The 30 Day visit will take place at 30days (-7 days, +14days) after the index procedure, and will include:

- Frailty Assessment by means of the following components: 5 meters walking time, grip strength, wasting and malnutrition (including blood sample to obtain Serum Albumin value) and cognitive impairment or dementia (via MMSE)
- Physical assessment
- 12 lead ECG
- Medication assessment
- Echocardiography
- NYHA functional classification
- QoL questionnaire (EQ-5D)

- 6MWT
- Modified Rankin Scale
- Adverse events assessment
- Device Deficiency assessment
- Permanent Pacemaker Control (if applicable)
- Resource utilization assessment

6.2.6. 1 Year follow-up visit (Cohort A only)

The 1 Year visit will take place at 365 days (\pm 90days) after the index procedure, and will include:

- Frailty Assessment by means of the following components: 5 meters walking time, grip strength, wasting and malnutrition (including blood sample to obtain Serum Albumin value) and cognitive impairment or dementia (via MMSE)
- Physical assessment
- 12 lead ECG
- Medication assessment
- Echocardiography
- NYHA functional classification
- QoL questionnaire (EQ-5D)
- 6MWT
- Modified Rankin Scale
- Adverse events assessment
- Device Deficiency assessment
- Resource utilization assessment

6.2.7. 2 Year follow-up visit

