7.4 Patient Death

7.4.1. Procedure for recording and reporting Patient Death

7.4.2. All patient deaths are to be documented and reported to the sponsor maximum 3 calendar days after becoming aware of the event. Should death occur, the investigator is requested to record death information in the hospital records and immediately document the information on the Death Form. By completing the form the sponsor will be notified. Refer to

and Appendix C: Data Collection Method. In case of EDC failure, notify Sponsor via Fax or via [contact].

All efforts (including use of national death registries) should be made to identify, precisely characterize, and appropriately classify any death.

Patient death is an outcome of a serious adverse event (SAE). All efforts to get SAE details should be made and the Adverse Event eCRF must be completed.

If available, the explanted Portico valve should be returned to SJM per instructions provided in Appendix K: Explant, Return, and Analysis of Valve and Appendix L: Instructions for device return - Large and Small Kits.

The patient's death is an early conclusion of the patient's participation in the investigation. Therefore, the investigator is requested to complete the termination form. The investigator must notify the EC/IRB, if appropriate, in accordance with national and local laws and regulations.

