9.3 Primary endpoint analysis

The primary endpoint analysis will only include patients from Cohort A.

Non-parametric survival analysis will be used to calculate the mortality rate at 1 year post index procedure and build its 95% confidence limit. The corresponding variance will be computed using Peto's formula for survival analysis. The survival time will be calculated as the number of days between the implant date and the death date for the patients who die at 1 year (365 days) post implant. And for the patients who are considered as censored (loss to follow up, explanted, etc.), the survival times will be calculated as the number of days between the implant date and the last known adverse event or the last documented contact date before 1 year follow up. A Kaplan-Meier curve with the cumulative survival rate will also be presented.

A Cox regression model can be used for further explanatory analysis of the relationship of the prognostic factors and the mortality. These factors will include baseline factors such as age, gender, NYHA class etc., and other factors defined by steering committee can also be analyzed.

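### Interim mortality reports have no data cut-off or follow-up condition, so under the written censoring rule interim 1-year mortality can be overstated

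*Combined protocol and SAP*

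**What the plan says.** - **Interim reports.** Section 9.5: "Interim reporting of primary and secondary endpoints will be performed" before the study ends, when the steering committee recommends it. It adds interim reporting for reimbursement at the request of a sponsor department. Section 5.3.2, like the synopsis, says: "Interim reporting at 30 days and 1-year all-cause mortality data may be performed on a subset of patients and compared with an appropriate external comparator". No section defines a cut-off date, the subset, or how long patients must have been followed.
- **Timing of deaths and survivors.** Section 9.3: "The survival time will be calculated as the number of days between the implant date and the death date". Censored patients run to the last known adverse event or last documented contact before the 1-year follow-up. For the safety secondary endpoints, 9.4 runs time to the first event, "or to the last documented contact date for the patients without the event".
- **Death reporting.** Section 7.4.1: "All patient deaths are to be documented and reported to the sponsor maximum 3 calendar days after becoming aware of the event". Sites are also told to use national death registries. No matching check on survivors is required.
- **Visits.** Section 6.2.5: "The 30 Day visit will take place at 30days (-7 days, +14days) after the index procedure", that is, days 23 to 44. The next scheduled visit (6.2.6) is at day 365 ± 90, so day 275 at the earliest. Later visits are yearly, with the same window.

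**The concern.** Kaplan-Meier estimation needs follow-up to be credited without regard to outcome. Take two patients on day 200 at an interim cut. The one who has died enters as a death on up to day 200. The one alive, with nothing recorded since the 30-day visit, is censored near day 30. Between visits the risk set loses survivors but keeps deaths, so the estimated hazard is too high. This concerns patients in normal follow-up, not dropouts, and a wider confidence interval does not correct it.

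The figure at stake is the one meant for reimbursement agencies, beside an external comparator. The error runs against the device.

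**Working it through.** **1. The plan's own figure, used as a yardstick (9.2.1).** Expected 1-year mortality is 22.1%, with 95% limits 18.8% to 25.4%, a half-width of 3.3 points.

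- n = 0.779 × 0.221 / (0.033/1.96)² = 607.3; the plan states 608.
- 608 / (0.779 × 0.9) = 867; the plan states 866.

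The plan states no figure for interim bias.

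**2. Inputs.**

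- From the documents: 22.1% mortality at 1 year; 866 patients; the visit windows; accrual of 2 years (9.2.1) or 3 years (section 5). These two accrual periods differ.
- Assumed: even accrual; 30-day mortality of 5% (range 3% to 8%) and a constant hazard thereafter; cuts at 24 and 36 months; all patients implanted so far are analysed; every death known at once; survivors contacted only at scheduled visits.

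**3. Hand calculation, visits on their nominal days.** Let C be the days from first implant to the cut, with accrual still open or just closed. At day t between 30 and 365:

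- deaths counted come from everyone implanted at least t days before the cut, proportional to C − t;
- the risk set holds those implanted at least 365 days before the cut, proportional to C − 365, plus newer patients who die before the cut, about h(365 − t)²/2.

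The hazard is therefore multiplied by R(t) = (C − t) / [(C − 365) + h(365 − t)²/2].

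The true cumulative hazard from day 30 to 365 is ln(0.95/0.779) = 0.1985, so h = 0.1985/335 = 0.000592 per day.

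| Cut | R(30) | R(197.5) | R(365) | Mean R (Simpson) | Reported 1-year mortality |
|---|---|---|---|---|---|
| C = 730 | 1.758 | 1.426 | 1.000 | 1.411 | 1 − 0.95·exp(−0.1985 × 1.411) = 28.2% |
| C = 1095, 3-year accrual | 1.395 | 1.216 | 1.000 | 1.210 | 1 − 0.95·exp(−0.1985 × 1.210) = 25.3% |

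With 30-day mortality of 3% and 8%, the same formula gives 28.7% and 27.3% at 24 months, and 25.6% and 24.8% at 36 months. The excess over 22.1% is about 5 to 7 points and about 3 points respectively.

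With 2-year accrual and a 36-month cut, every patient was implanted at least 365 days earlier. R is then 1 and the bias is 0.

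**4. Simulation with visits spread over their windows** (300,000 to 400,000 patients per scenario):

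- 24 months: +6.6 to +8.4 points, whichever accrual period applies.
- 36 months: +3.3 to +4.3 with 3-year accrual, about +1 with 2-year accrual.
- 48 months: 0 to +0.7.
- 30-day mortality: at most about +0.5 at any cut.
- 2-year mortality: +6 to +10 at 36 months and +0.7 to +4 at 48 months, if the first-year hazard persists.
- Final analysis with complete follow-up: 0.

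**5. Sensitivity, 1-year mortality at 24 months:**

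- share of deaths known at once: 75% gives +5.7, 50% gives +4.0, and none until the next scheduled visit gives 0;
- extra survivor contacts per year (constant hazard): 2 give +4.1, 4 give +2.6, 12 give +1.0.

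**6. Remedies tested.** Crediting survivors to a common cut at which vital status is confirmed gives 22.0% to 22.2%. Restricting to patients implanted at least 455 days before the cut, with the censoring rule unchanged, leaves about 0.4 to 1.1 points (up to about 1.5 across all hazard shapes tried). The reason is that a patient seen on days 275 to 364 is still censored before day 365, while a later death in that interval counts.

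**The case against.** A reader might infer that the plan prescribes counting deaths to a data cut and survivors to their last visit, and that interim mortality will therefore always be several points too high. The documents do not support that.

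- **No cut is defined, and the censoring point is not the last visit.** Section 9.3 accepts a last known adverse event, and its examples of censored patients are losses and explants, not patients still in follow-up. This stands as a limit on wording. The asymmetry remains, because no other rule exists for an interim report.
- **Survivors are updated between visits.** Section 7.3.2 puts serious adverse events and device effects on the same 3-day clock and also collects non-serious cardiovascular and neurovascular events. Section 6.2.11 records unscheduled visits. This reduces the bias, as step 5 shows, but only for patients who have such contacts.
- **The 3 days run from awareness, not from death.** If deaths surfaced only at visits, there would be no bias. Use of national registries makes that unlikely to hold throughout.
- **A subset is already allowed.** It could be a mature one, but nothing says so.
- **The separate SAP might cover this.** Section 9.4 refers other secondary analyses to it; no interim cut-off rule is promised there.
- **Consequences are limited.** The study is single-arm and aims at estimation, no interim decision rule is stated, and the final analysis is unaffected. This stands, and keeps the point below the most serious level.

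**Conclusion.** The concern holds in conditional form. Sections 9.3 and 9.4 give the only timing rule, and 9.5 reports the same endpoints at interim without a cut-off or maturity condition. Followed as written, interim 1-year mortality can be overstated. With a true rate of 22.1%, the excess is up to about 5 to 8 points at 24 months. At 36 months it is 3 to 4 points with 3-year accrual and about 0 to 1 with 2-year accrual. The upper figures assume that all implanted patients are analysed, that deaths are known at once and that survivors have scheduled contacts only. At 24 months they exceed the planned half-width of 3.3 points; under milder assumptions the excess falls below it. The newest landmark at later cuts can be affected in the same way. The sponsor should settle this before the first interim report.

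**What to change.** Add to 9.5 or the SAP:

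1. Each interim report uses one common cut-off date for deaths and survivors.
2. A k-year estimate includes only patients implanted at least 365k + 90 days before that date (455 days for 1 year), and the 30-day estimate only those implanted at least 44 days before. Selection is by implant date, never by outcome.
3. For included patients whose k-year visit fell before day 365k, confirm vital status at or after day 365k and credit survivors to that date. The filter alone does not remove the whole error.

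**Cost.** Some text, a date filter, and a status query for the early-visit patients. Interim samples shrink. With 3-year accrual, a 24-month cut keeps 866 × (730 − 455)/1095 ≈ 218 of 866 × 730/1095 ≈ 577 patients, with half-width 1.96 × √(0.221 × 0.779/218) ≈ 5.5 points. A 36-month cut keeps 866 × (1095 − 455)/1095 ≈ 506 of 866, with half-width about 3.6 points. The final analysis does not change.
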